9.6 Reporting Procedures for All Adverse Events

All local and systemic AEs occurring in the 28 days following each vaccination observed by the Investigator or reported by the volunteer, whether or not attributed to study medication, will be recorded. Recording and reporting of all AEs will take place as detailed in the relevant SOP. All AEs that result in a volunteer's withdrawal from the study will be followed up until a satisfactory resolution occurs, or until a non-study related causality is assigned (if the volunteer consents to this). Serious adverse events (SAEs) will be collected throughout the entire trial period.

9.6.1 Reporting Procedures for Serious AEs

In order to comply with current regulations on serious adverse event reporting to regulatory authorities, the event will be documented accurately and notification deadlines respected. SAEs will be reported on the SAE forms to members of the study team immediately the Investigators become aware of their occurrence, as described in relevant safety reporting SOPs. Copies of all reports will be forwarded for review to the Chief Investigator (as the Sponsor's representative) within 24 hours of the Investigator being aware of the suspected SAE. The local safety monitor (LSM) will be notified of SAEs that are deemed possibly, probably or definitely related to study interventions; the LSM will be notified immediately (within 24 hours) of the Investigators' being aware of their occurrence. SAEs will not normally be reported immediately to the ethical committee(s) unless there is a clinically important increase in occurrence rate, an unexpected outcome, or a new event that is likely to affect safety of trial volunteers, at the discretion of the Chief Investigator and/or LSM. In addition to the expedited reporting above, the Investigator shall include all SAEs in the annual Development Safety Update Report (DSUR) report.

9.6.2 Reporting Procedures for SUSARS

The Chief Investigator will report all SUSARs to the MHRA and ethical committee(s) within required timelines (15 days for all SUSARs, unless life threatening in which case 7 days, with a final report within a further 8 days (total 15). The Chief Investigator will also inform all Investigators concerned of relevant information about SUSARs that could adversely affect the safety of participants. All SUSARs and deaths occurring during the study will be reported to the Sponsor. For all deaths, available autopsy reports and relevant medical reports will be made available for reporting to the relevant authorities.

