9.2.3 Unexpected Adverse Reaction

An adverse reaction, the nature or severity of which is not consistent with the applicable product information (e.g. IB for an unapproved IMP).

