9.2.4 Serious Adverse Event (SAE)

A SAE is an AE that results in any of the following outcomes, whether or not considered related to the study intervention.

- Death
- Life-threatening event (i.e., the volunteer was, in the view of the Investigator, at immediate risk of death from the event that occurred). This does not include an AE that, if it occurred in a more severe form, might have caused death.
- Persistent or significant disability or incapacity (i.e., substantial disruption of one's ability to carry out normal life functions).
- Hospitalisation, regardless of length of stay, even if it is a precautionary measure for continued observation. Hospitalisation (including inpatient or outpatient hospitalisation for an elective procedure) for a pre-existing condition that has not worsened unexpectedly does not constitute a serious AE.
- An important medical event (that may not cause death, be life threatening, or require hospitalisation) that may, based upon appropriate medical judgment, jeopardise the volunteer and/or require medical or surgical intervention to prevent one of the outcomes listed above. Examples of such medical events include allergic reaction requiring intensive treatment in an emergency room or clinic, blood dyscrasias, or convulsions that do not result in inpatient hospitalisation.
- Congenital anomaly or birth defect.

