9.2.6 Suspected Unexpected Serious Adverse Reaction (SUSAR)

A serious adverse reaction, the nature and severity of which is not consistent with the information about the medicinal product in question set out in the IB.

9.3 Foreseeable Adverse Reactions:

The foreseeable ARs following vaccination with MVA NP+M1 include injection site pain, erythema, warmth, swelling, pruritus, myalgia, arthralgia, headache, fatigue, fever, feverishness, malaise, nausea, muscular and articular pain.

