9.4 Expected Serious Adverse Events

No serious adverse events are expected in this study.

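### The SUSAR definition is narrower than the protocol's definition of unexpected, and the 7-day reporting clock does not say whether it covers fatal SUSARs

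*Protocol*

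**What the plan says.** **The clock.** Section 9.6.2 opens with a general commitment, "The Chief Investigator will report all SUSARs to the MHRA and ethical committee(s) within required timelines", and then spells the timelines out in a bracket: "15 days for all SUSARs, unless life threatening in which case 7 days, with a final report within a further 8 days". On deaths, the same section says "All SUSARs and deaths occurring during the study will be reported to the Sponsor" and that autopsy and medical reports will be made available. It attaches no number of days to either statement.

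**The categories.** Section 9.2.4 introduces its list with "A SAE is an AE that results in any of the following outcomes". Death is one bullet. Another begins "Life-threatening event (i.e., the volunteer was, in the view of the Investigator, at immediate risk of death from the event that occurred". Section 9.10 likewise gives a related death and a related life-threatening reaction their own holding-rule bullets.

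**Expectedness.** Section 9.2.3 defines an unexpected reaction as "An adverse reaction, the nature or severity of which is not consistent with the applicable product information", and gives the IB as the example of such information for an unapproved product. Section 9.2.6 defines a SUSAR as "A serious adverse reaction, the nature and severity of which is not consistent with the information about the medicinal product in question", again with reference to the IB. Section 9.4 states: "No serious adverse events are expected in this study".

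**The concern.** SUSAR status and the clock in 9.6.2 together decide what reaches the MHRA and the ethics committee quickly. An event that is not a SUSAR falls back on section 9.6.1. There, SAEs do not normally go to the ethics committee at once, apart from listed exceptions that the Chief Investigator or the safety monitor may invoke at their discretion.

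The two faults are separate. A one-word difference between 9.2.3 and 9.2.6 can take a serious reaction out of the expedited route altogether. The silence on fatal SUSARs in 9.6.2 leaves it to the reader which of two clocks applies to a death. Both matter more than usual here, because this is the first use in humans of the vaccine made on the new cell line, and its safety result decides whether a phase IIb trial with 1000 recipients goes ahead (section 3.8).

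**Working it through.** No sample-size or power figure is involved. The check is one sum and a comparison of passages.

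**1. The plan's own figure.** Inputs from 9.6.2: 7 days for a life-threatening SUSAR, a further 8 days to its final report, and a 15-day default. 7 + 8 = 15 days, which agrees with the total printed in the protocol.

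**2. Which clock applies to a fatal SUSAR.**

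- SUSAR classed as life-threatening: first report by day 7, final report by day 15.
- Fatal SUSAR that the investigator also classes as life-threatening: day 7.
- Fatal SUSAR classed only under death: no exception applies, so day 15.

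The gap between the last two is 15 − 7 = 8 days. Nothing in 9.2.4, 9.6.2 or 9.10 says which classification is to be used.

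**3. Expectedness, case by case, for a serious adverse reaction.**

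| Nature fits the IB? | Severity fits the IB? | Unexpected under 9.2.3 (either fails) | SUSAR under literal 9.2.6 (both fail) |
|---|---|---|---|
| No | No | Yes | Yes |
| Yes | No | Yes | **No** |
| No | Yes | Yes | **No** |
| Yes | Yes | No | No |

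The definitions disagree in the two middle rows. The second row is the practical one: a reaction of a type the IB describes, but more severe than described there. It is serious, suspected and unexpected by 9.2.3, yet literally not a SUSAR, so 9.6.2 does not reach it.

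**4. Against section 9.4.** If no serious event is expected, one would look for serious reactions to be unexpected. Literal 9.2.6 can nevertheless refuse that label to a serious reaction whose nature is in the IB. Section 9.4 does not say how it relates to the IB test.

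**5. What else happens after such an event.** Under 9.10, any related SAE, life-threatening reaction or death meets a holding rule, whether or not it is a SUSAR. Restarting requires a substantial-amendment request to the regulatory authority, and the ethics committee and manufacturers are told of the hold, with no deadline given. Sections 9.6.1 and 9.9 require notice of related SAEs to the Local Safety Monitor (LSM) and Local Safety Committee (LSC) within 24 hours. So the consequence in steps 2 and 3 is confined to the expedited report itself.

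**The case against.** **Death and life-threatening are not declared exclusive.** A volunteer who dies of an event would ordinarily also have met the life-threatening definition. Separate bullets do not prove otherwise: 9.10 also gives SAEs a bullet of their own, although both other categories are SAEs under 9.2.4, so that list plainly overlaps. This stands. A reader might infer that the protocol deliberately reports the worst outcome more slowly; the text does not support that. What remains is an ambiguity that permits the slower clock.

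**Outside rules govern.** Section 9.6.2 speaks of required timelines, and 9.6.1 and 12.2 commit to the applicable regulations. That softens the point, but the bracket tells staff what those timelines are and leaves fatal events out. What the regulations demand is not in the document and is not relied on here.

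**The definition in 9.2.6 can be read kindly.** One may take nature and severity as a joint profile that fails to match if either element fails. That reading is possible, but 9.2.3 uses the other conjunction for the same idea, and a reporting rule should not need the kinder reading.

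**The range of affected reactions.** A reader might infer that a serious form of every foreseeable reaction in 9.3 escapes. That does not follow: 9.2.6 tests against the IB, which is not at hand, and not against the list in 9.3.

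**Dosing is protected.** This largely stands, as step 5 of the working shows. A reader might infer that vaccination could continue during a late report; the holding rules do not allow it. The discretionary exceptions in 9.6.1, which include an unexpected outcome, could also bring such a case to the ethics committee early.

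**Section 9.4 settles everything.** A reader might infer from it that every serious adverse reaction is automatically a SUSAR. The protocol does not say so, and such a rule would bypass the IB test in 9.2.6.

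**Conclusion.** The point holds in two limited parts. First, 9.2.3 and 9.2.6 conflict: where only one of nature and severity departs from the IB, a serious reaction is unexpected under the one and literally not a SUSAR under the other, and so falls outside 9.6.2. Second, 9.6.2 is ambiguous for fatal SUSARs: one classed only under death would literally be due up to 8 days later than a life-threatening one.

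The 8 days assume that classification and reporting on the last permitted day. The definitional conflict assumes a literal reading of the conjunction in 9.2.6. Such events are unlikely in six volunteers; section 3.6 reports no vaccine-related SAE in 145 recipients of the vaccine made on chick cells, but also a severe fever with fatigue and malaise in one recipient of another MVA vaccine made on the new cell line. The effect is on expedited reporting to the MHRA and ethics committee. No endpoint, analysis or sample-size figure changes. Correcting the wording is worthwhile because it costs almost nothing and the product is new in humans.

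**What to change.** 1. In 9.2.6, replace *and* with *or* between nature and severity, so that the SUSAR definition matches 9.2.3.
2. In 9.6.2, name fatal SUSARs explicitly beside life-threatening ones in the shorter clock, and reconcile that sentence with the categories in 9.2.4 and 9.10.
3. Reconcile 9.4 with 9.2.6 by stating whether 9.4 has any bearing on the expectedness test or whether the IB alone decides. Do not add a blanket rule that every serious adverse reaction is a SUSAR.

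The cost is a few words in 9.2.6 and 9.6.2 and one clarifying sentence for 9.4. No visit, sample, form or analysis is added.

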9.6.3 Development Safety Update Report

A Development Safety Update Report (DSUR) will be submitted by the Sponsor to the competent authority and ethical committee on the anniversary of the first approval date from the regulatory authority for each IMP.

9.7 Assessment of severity

The severity of clinical and laboratory adverse events will be assessed according to the scales in Table 6 -Table 8.

CONFIDENTIAL

Adverse Event	Grade	Intensity
Erythema at injection site*	1	>3 - ≤50 mm
	2	>50 - ≤100 mm
	3	>100 mm
Swelling at injection site	1	>3 - ≤20 mm
	2	>20 - ≤50 mm
	3	>50 mm
Ulceration/necrosis of skin at injection site	1	-
	2	-
	3	Any

Table 6. Severity grading criteria for local adverse events

*erythema or swelling ≤3mm is an expected consequence of skin puncture and will therefore not be considered an adverse event.

Table 7. Severity grading criteria for physical observations.	

	Grade 1 (mild)	Grade 2 (moderate)	Grade 3 (severe)
Fever (oral)	37.6°C - 38.0°C	38.1°C – 39.0°C	>39.0°C
Tachycardia (bpm)*	101 - 115	116 - 130	>130
Bradycardia (bpm)**	50 – 54	40 - 49	<40
Systolic hypertension (mmHg)	141 - 159	160 - 179	≥180
Systolic hypotension (mmHg)***	85 - 89	80 - 84	<80
Diastolic hypertension (mmHg)	91 - 99	100 - 109	≥110

*Taken after ≥10 minutes at rest

**Use clinical judgement when characterising bradycardia among some healthy subject populations, for example, conditioned athletes.

***Only if symptomatic (e.g. dizzy/ light-headed)

GRADE 0	None: Symptom not experienced	
GRADE 1	Mild: Short-lived or mild symptoms; medication may be required. No limitation to usual activity	
GRADE 2	Moderate: Mild to moderate limitation in usual activity. Medication may be required.	
GRADE 3	Severe: Considerable limitation in activity. Medication or medical attention required.	

Table 8. Severity grading criteria for local and systemic AEs.

9.8 Procedures to be followed in the event of abnormal findings

Laboratory parameters for inclusion/exclusion in the trial will be considered on an individual basis, with investigator discretion for interpretation of results and the need for repeated tests. In general, volunteers will be excluded if a result at screening constitutes what would qualify as a grade 1 (or higher) laboratory adverse event, according to the site-specific laboratory adverse event tables (stored in TMF or ISF). Abnormal clinical findings from medical history, examination or blood tests will be assessed as to their clinical significance throughout the trial. If a test is deemed clinically significant, it may be repeated, to ensure it is not a single occurrence. If a test remains clinically significant, the volunteer will be informed and appropriate medical care arranged as appropriate and with the permission of the volunteer. Decisions to exclude the volunteer from enrolling in the trial or to withdraw a volunteer from the trial will be at the discretion of the Investigator.

9.9 Local Safety Committee

A Local Safety Committee (LSC) will be appointed to provide real-time safety oversight. The LSC will review SAEs deemed possibly, probably or definitely related to study interventions. The LSC will be notified within 24 hours of the Investigators' being aware of their occurrence. The LSC has the power to place the study on hold if deemed necessary following a study intervention-related SAE. At the time of writing the LSC will be chaired by [name], a Clinical Tutor in Medicine, Honorary Consultant Physician and Director, Centre for Tropical Medicine at the University of Oxford. There will be a minimum of two other appropriately qualified committee members. All correspondence between Investigator and LSC will be conveyed by the Investigator to the trial Sponsor.

The chair of the LSC may be contacted for advice and independent review by the Investigator or trial Sponsor in the following situations:

• Following any SAE deemed to be possibly, probably, or definitely related to a study intervention.

• Any other situation where the Investigator or trial Sponsor feels independent advice or review is important.

9.9.1 Safety Profile Review

The safety profile will be assessed on an on-going basis by the Investigators. The LSC will perform independent external safety reviews after vaccination of the first 3 volunteers. The Chief investigator and relevant Investigators (as per the trial delegation log) will also review safety issues and SAEs as they arise.

9.10 Safety Holding Rules

Safety holding rules have been developed considering the fact this is the first time the MVA-NP+M1 vaccine, developed on the novel immortalised duck retinal cell line AGE1.CR.pIX, is used. 'Solicited adverse events' are those listed as foreseeable adverse events in section 9 of the protocol, occurring within the first 7 days after vaccination (day of vaccination and six subsequent days). 'Unsolicited adverse events' are adverse events other than the foreseeable AEs occurring within the first 7 days or any AEs occurring after 7 days post vaccination.

The group holding rules are as follows:

- Solicited local adverse events: If 2 or more volunteers present the same Grade 3 solicited local adverse event beginning within 2 days after vaccination (day of vaccination and one subsequent day) and persisting at Grade 3 for >48 hrs
- Solicited systemic adverse events: If 2 or more volunteers present the same Grade 3 solicited systemic adverse event beginning within 2 days after vaccination (day of vaccination and one subsequent day) and persisting at Grade 3 for >48hrs.
- Unsolicited adverse events: If 2 or more volunteers develop the same Grade 3 unsolicited adverse event (including the same laboratory adverse event) that is considered possibly, probably or definitely related to vaccination and persists at Grade 3 for >48hrs.
- A life-threatening reaction considered possibly, probably or definitely related to vaccination occurs
- A serious adverse event considered possibly, probably or definitely related to vaccination occurs

• Death considered possibly, probably or definitely related to vaccination

If a volunteer has an acute illness (moderate or severe illness with or without fever) or a fever (oral temperature greater than 37.5°C) at the scheduled time of administration of investigational product, the volunteer will not receive the vaccine at that time. The vaccine may be administered to that volunteer at a later date within the time window specified in the protocol (see Table 4) or they may be withdrawn from the study at the discretion of the Investigator.

If a holding rule has been met and following an internal safety review it is deemed appropriate to restart dosing, a request to restart dosing with pertinent data must be submitted to the regulatory authority as a request for a substantial amendment. The internal safety review will consider:

- The relationship of the AE or SAE to the vaccine.
- The relationship of the AE or SAE to the vaccine dose, or other possible causes of the event.
- If appropriate, additional screening or laboratory testing for other volunteers to identify those who may develop similar symptoms and alterations to the current Participant Information Sheet (PIS) are discussed.
- New, relevant safety information from ongoing research programs on the various components of the vaccine.

The local ethics committee and vaccine manufacturers will also be notified if a holding rule is activated or released.

All vaccinated volunteers will be followed for safety reasons until resolution or stabilization (if determined to be chronic sequelae) of their AEs.

In addition to the pre-defined criteria, the study can be put on hold upon advice of the Local Safety Monitor, Chief Investigator, Study Sponsor, regulatory authority, Ethical Committee(s) or Local Safety Committee, for any single event or combination of multiple events which, in their professional opinion, jeopardise the safety of the volunteers or the reliability of the data.

10 STATISTICS

Sample Size Selection and Statistical analysis

This is a descriptive safety study, where volunteers will be vaccinated with MVA-NP+M1 alone. A maximum of 6 volunteers will be vaccinated in total. Safety data will be presented according to frequency, severity and duration of adverse events. This sample size should

allow an initial estimation to be made of the frequency and magnitude of outcome measures.

Non-parametric tests will be used to determine differences in the primary immunogenicity outcome (ELISpot) data, testing for differences in responses between time points within a group.

11. QUALITY CONTROL AND QUALITY ASSURANCE PROCEDURES

11.1 Investigator procedures

Approved site-specific standard operating procedures (SOPs) will be used at clinical and laboratory sites.

11.2 Monitoring

Monitoring will be performed independently, according to ICH GCP. The monitors will verify that the clinical trial is conducted and data are generated, documented and reported in compliance with the protocol, GCP and the applicable regulatory requirements. The site will provide direct access to all trial related source data/documents and reports for the purpose of monitoring and auditing by the Sponsor and inspection by local and regulatory authorities.

11.3 Modification to protocol

No substantial amendments to this protocol will be made without consultation with, and agreement of the Sponsor. Any substantial amendments to the trial that appear necessary during the course of the trial must be discussed by the Investigator and Sponsor concurrently. If agreement is reached concerning the need for an amendment, it will be produced in writing by the Chief Investigator and will be made a formal part of the protocol following ethical and regulatory approval.

The Investigator is responsible for ensuring that changes to an approved trial, during the period for which regulatory and ethical committee(s) approval has already been given, are not initiated without regulatory and ethical committee(s)' review and approval except to eliminate apparent immediate hazards to the subject.

11.4 Protocol deviation

Any deviations from the protocol will be documented in a protocol deviation form and filed in the trial master file.

11.5 Audit & inspection

The QA manager may perform internal audits to check that the trial is being conducted; data recorded, analysed and accurately reported according to the protocol, Sponsor's SOPs and in compliance with ICH GCP. The audits will also include laboratory activities according to an

agreed audit schedule. The internal audits will supplement the external monitoring process and will review processes not covered by the external monitor.

The Sponsor, trial sites, and ethical committee(s) may carry out audit to ensure compliance with the protocol, GCP and appropriate regulations. GCP inspections may also be undertaken by the MHRA to ensure compliance with protocol and the Medicines for Human Use (Clinical Trials) Regulations 2004. The Sponsor will assist in any inspections and will formally respond to the MHRA as part of the inspection procedure.

